o. Subject Population(s) for Analysis

- All-randomized population.
- All-treated population
- Protocol-compliant population

11. Safety and Adverse Events (as stated in the IRB template)

p. Definitions

i. Adverse Event

An adverse event (AE) is any symptom, sign, illness or experience that develops or worsens in severity during the course of the study. Illnesses or injuries will be regarded as adverse events. Abnormal results of diagnostic procedures are considered to be adverse events if the abnormality:

- results in study withdrawal
- is associated with a serious adverse event
- is associated with clinical signs or symptoms
- leads to additional treatment or to further diagnostic tests
- is considered by the investigator to be of clinical significance

ii. Serious Adverse Event

Serious Adverse Event

Adverse events are classified as serious or non-serious. A serious adverse event is any AE that is:

- fatal
- life-threatening
- requires or prolongs hospital stay
- results in persistent or significant disability or incapacity
- a congenital anomaly or birth defect
- an important medical event

Important medical events are those that may not be immediately life threatening but are clearly of major clinical significance. They may jeopardize the subject and may require intervention to prevent one of the other serious outcomes noted above. For example, drug overdose or abuse, a seizure that did not result in in-patient hospitalization, or intensive treatment of bronchospasm in an emergency department would typically be considered serious.

All adverse events that do not meet any of the criteria for serious should be regarded as **non-serious adverse events**.

q. Recording of Adverse Events

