At each contact with the subject, the investigator will seek information on adverse events by specific questioning and, as appropriate, by examination. Information on all adverse events will be recorded immediately in the source document, and also in the appropriate adverse event module of the case report form (CRF). All clearly related signs, symptoms, and abnormal diagnostic procedures results will be recorded in the source document, though grouped under one diagnosis. All adverse events occurring during the study period will be recorded. The clinical course of each event will be followed until resolution, stabilization, or until it has been determined that the study intervention or participation is not the cause. Serious adverse events that are still ongoing at the end of the study period will be followed up to determine the final outcome. Any serious adverse event that occurs after the study period and is considered to be possibly related to the study intervention or study participation will be recorded and reported immediately.

r. Relationship of AE to Study

The relationship of each adverse event to the study procedures will be classified in terms of the event's potential relationship to the study (definitely related, probably related, possibly related, unlikely or unrelated).

s. Reporting of Adverse Events, Adverse Device Effects and Unanticipated Problems

The occurrence of adverse events will be reported to the study's medical collaborators, advisory board chair, Penn IRB, and our contacts at Axsome.

If the report is supplied as a narrative, the minimum necessary information to be provided at the time of the initial report includes:

- *Study identifier*
- *Study Center*
- *Subject number*
- *A description of the event*
- *Date of onset*
- *Current status*
- *Whether study intervention was discontinued*
- *The reason why the event is classified as serious*
- *Investigator assessment of the association between the event and study intervention*

Additionally all other events (unanticipated problems, adverse reactions, unanticipated adverse device effects and subject complaints) will be recorded and reported with respect to institutional and federal policies as described in the Penn Manual and below.

i. Follow-up report

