If an SAE has not resolved at the time of the initial report and new information arises that changes the investigator's assessment of the event, a follow-up report including all relevant new or reassessed information (e.g., concomitant medication, medical history) will be submitted to the IRB. The investigator will be responsible for ensuring that all SAE are followed until either resolved or stable.

ii. Investigator reporting: notifying the study sponsor

Any study-related unanticipated problem posing risk to subjects or others, and any type of serious adverse event, will be reported to the study sponsor (Axsome) by telephone and email within 24 hours of the event. Specifically, the SAE will be reported to our program officer. *"To report such events, a Serious Adverse Event (SAE) form will be completed by the investigator and faxed to the study sponsor within 24 hours. The investigator will keep a copy of this SAE form on file at the study site. Report serious adverse events to the therapist, CRC, and/or the PI via e-mail or phone*

Study PI: [name], [contact],
CRC: [name], [contact]

Within the following 48 hours, the investigator will provide further information on the serious adverse event or the unanticipated problem in the form of a written narrative. This will include a copy of the completed Serious Adverse Event form, and any other diagnostic information that will assist the understanding of the event. Significant new information on ongoing serious adverse events will be provided promptly to the study sponsor.

t. Investigator Reporting: Notifying the Penn IRB

Penn IRB will be notified in accordance with the requirements and timelines as specified by the IRB.

i. Sponsor reporting: Notifying the FDA (applies only to Penn sponsor –investigator IND/IDE holders)
N/A

ii. Sponsor reporting: Notifying participating investigators N/A

u. Unblinding Procedures

In the event of an SAE, Investigational Drug Services of the University of Pennsylvania will unblind the subject's status with respect to treatment condition. This information will be provided to the subject, and with permission, the subject's clinical providers (or emergency care providers) within 24 hours or less.

v. Stopping Rules

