The advisory board chair will be notified of any serious adverse events that occur, regardless of whether they are thought to be study-related, within 24 hours of project staff learning of their occurrence. The advisory board chair will decide, independent of the study investigators, whether the study should be discontinued.

w. Medical Monitoring

The medical monitoring will be accomplished by our collaborating physician, [name].

i. Data and Safety Monitoring Plan

Please see below.

Data Safety Monitoring Board

We will establish a four-person advisory board comprised of a second MD sleep medicine specialist, clinical psychologist, a nurse sleep scientist, and a biostatistician. Membership consists of persons completely independent of the investigators who have no financial, scientific, or other conflicts of interest with the trial. Collaborators of the PIs will not be eligible to

serve on the advisory board. The board will receive reports from the study team every six months with information about the progress of recruitment, the demographic characteristics of participants, serious adverse events, the number of dropouts, and participants' reasons for dropping out, and any protocol amendments. These meetings will focus on the conduct and progress of the study, including participant accrual, protocol compliance, and problems encountered.

12. Study Administration, Data Handling and Record Keeping

x. Confidentiality

Information about study subjects will be kept confidential and managed according to the requirements of the Health Insurance Portability and Accountability Act of 1996 (HIPAA). In the event that a subject revokes authorization to collect or use PHI, the investigator, by regulation, retains the ability to use all information collected prior to the revocation of subject authorization. For subjects that have revoked authorization to collect or use PHI, attempts will be made to obtain permission to collect at least vital status (i.e. that the subject is alive) at the end of their scheduled study period.

In the case of the present study all self-report data will be acquired through RedCap and Hypknowledge. Files containing PHI (that is not stored in the EMR) will be stored on a secure shared drive on the Penn Network. Only authorized study staff will have access to this shared drive.

y. Data Collection and Management

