All data will be collected via Redcap and Hypknowledge. Data download will only be available to the PI and/or his designates. Files containing PHI will be stored on a secure shared drive on the Penn network. Only authorized study staff will have access to this shared drive.

z. Records Retention

All electronic data will be maintained for a period equal to that required by the study sponsor. Longer term database management will occur, but all subject identifiers will be removed.

13. Study Monitoring, Auditing, and Inspecting

The study materials and databases will be available to the study sponsor, the advisory board, and/or Penn IRB should a data audit be deemed necessary.

aa. Study Monitoring Plan

See DSMB section.

bb. Auditing and Inspecting

The investigator will permit study-related monitoring, audits, and inspections by the EC/IRB, the sponsor, government regulatory bodies, and University compliance and quality assurance groups of all study related documents (e.g. source documents, regulatory documents, data collection instruments, study data etc.). The investigator will ensure the capability for inspections of applicable study-related facilities (e.g. pharmacy, diagnostic laboratory, etc.). Participation as an investigator in this study implies acceptance of potential inspection by government regulatory authorities and applicable University compliance and quality assurance offices.

14. Ethical Considerations

This study is to be conducted in accordance with applicable US government regulations and international standards of Good Clinical Practice, and applicable institutional research policies and procedures.

This protocol and any amendments will be submitted to a properly constituted independent Ethics Committee (EC) or Institutional Review Board (IRB), in agreement with local legal prescriptions, for formal approval of the study conduct. The decision of the EC/IRB concerning the conduct of the study will be made in writing to the investigator and a copy of this decision will be provided to the sponsor before commencement of this study.

cc. Risks

Risks of Cognitive Behavioral Therapy for Insomnia (CBT-I):

CBT-I may result in temporary increases in daytime fatigue and/or sleepiness, and/or memory and concentration difficulties.

dd. Risks of Solriamfetol:

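### Any SAE, related or not, automatically discloses the drug allocation to the subject whose diary is the primary endpoint, while no provision gives it to the advisory board chair

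*Combined protocol and SAP*

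**What the plan says.** Section 11.u sets the rule: "In the event of an SAE, Investigational Drug Services of the University of Pennsylvania will unblind the subject's status with respect to treatment condition". It then names the recipients: "This information will be provided to the subject, and with permission, the subject's clinical providers (or emergency care providers) within 24 hours or less". Nobody else is listed.

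An SAE is defined in section 11.p as an adverse event meeting one of several criteria, among them that it "requires or prolongs hospital stay". Illnesses and injuries count as adverse events. Section 11.r grades relatedness in five levels ("definitely related, probably related, possibly related, unlikely or unrelated"), but 11.u does not use that grading.

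On stopping, section 11.v says: "The advisory board chair will be notified of any serious adverse events that occur, regardless of whether they are thought to be study-related". Notice is due no later than 24 hours after staff learn of the event. It continues: "The advisory board chair will decide, independent of the study investigators, whether the study should be discontinued".

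The trial is described as double blind (section 5, General Design). The primary hypothesis compares solriamfetol with placebo (section 5.6). The primary endpoint is total wake time from a web-based self-report diary (section 10.k), and the primary analysis is by intention to treat (section 10.n).

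**The concern.** The capsule blind is what protects the primary comparison. Subjects necessarily know whether they receive CBT-I, so the drug factor is the only one that can be concealed from them, and it is the factor that 11.u discloses. A subject who learns that the capsules were solriamfetol, or placebo, may then report wake time differently. The plan does not say how diary data after unblinding are to be handled.

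Clinical need does not explain the rule. The subject is told in every case, whereas treating and emergency providers, who might need the code, receive it only with the subject's permission.

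The person charged with the stopping decision has no stated route to the allocation, although whether an SAE occurred on drug or placebo is central to that decision.

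**Working it through.** **Trigger.** Setting 11.p, 11.r and 11.u side by side: a fracture during the capsule period is an injury and so an adverse event; if it requires admission it is serious; it may be graded unrelated; and 11.u still requires the code break. The five-level grading exists but has no role in the rule.

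**Recipient.** The first recipient in 11.u is the person who produces the section 10.k endpoint. Under section 10.n that person's later diaries stay in the primary analysis.

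**Chair.** Four places could give the chair the allocation:
- 11.u: the chair is not a named recipient.
- 11.s: allocation is not in the minimum content of an SAE narrative.
- 11.w.i: "The board will receive reports from the study team every six months with information about the progress of recruitment", demographics, SAEs, dropouts and amendments; allocation is not listed.
- Section 13: "The study materials and databases will be available to the study sponsor, the advisory board, and/or Penn IRB should a data audit be deemed necessary". This access is conditional and is tied neither to SAEs nor to the code.

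**Yardstick: the plan's own sample size.** Section 10.m gives 30 minutes, SD 19, four groups, alpha 0.05, 80% power and 10 per group. Take a one-way ANOVA with two means 30 minutes apart and the other two at the midpoint. The sum of squared deviations is 15² + 15² = 450, and the noncentrality is n × 450 / 19². Power is 75.8% at n = 9 and 81.1% at n = 10, so 10 per group reproduces. Recruiting 60 to complete 40 implies 20/60 = 33.3% attrition.

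**Expected number of events.** The documents give no SAE rate, so 1-3% per subject is assumed.
- Expected subjects with an SAE: 60 × 0.01 = 0.6 to 60 × 0.03 = 1.8.
- Chance of at least one: 1 − 0.99^60 = 45% to 1 − 0.97^60 = 84%.
- If these subjects completed at the plan's overall rate (40/60), 0.4 to 1.2 would supply post-treatment diaries.

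**Effect on the primary comparison.** Assume each unblinded subject's diary shifts by 10 to 30 minutes; the documents give no figure for this either. The shift in a mean is m × s / n, where m is the number unblinded, s the shift and n the number averaged.
- Generous case: all 0.6 to 1.8 subjects complete and split evenly, so 0.3 to 0.9 fall in each drug level of 20. The level mean moves by 0.3 × 10 / 20 = 0.15 to 0.9 × 30 / 20 = 1.35 minutes.
- If the two levels shift in opposite directions, the contrast moves by twice that: 0.3 to 2.7 minutes.
- Unlucky case: three unblinded subjects in one drug level, each shifted by 30 minutes, move its mean by 3 × 30 / 20 = 4.5 minutes. All three in one arm of 10 move that arm by 9 minutes.

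The reference is the 30-minute target difference.

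**Cost of excluding affected diaries.** Losing one subject from every group (four in all) lowers power from 81.1% to 75.8%. The expected loss is smaller than that.

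**The case against.** The strongest reply is that telling a subject after a serious event is a defensible safety-first choice, that SAEs will be few, and that many affected subjects will not reach the post-treatment diary, since section 8.e allows discontinuation for adverse events. The reply on numbers stands: 45-84% is only the chance of at least one SAE at an assumed rate, not the chance of a biased result. The safety argument does not rescue the rule as written, because the rule ignores care need and puts a permission step in front of the clinicians but not the subject.

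A reader might infer more than the documents support:
- *Any hospital stay, even elective, breaks the blind.* An SAE must first be an adverse event, which under 11.p develops or worsens during the study. An elective admission for a stable condition does not qualify.
- *The rule also applies in the 2-week baseline.* Section 5.1 places those diaries before enrolment and the timing of randomisation is not stated, so there may be no code to break.
- *Staff are unblinded.* 11.u does not name the investigator, therapist or coordinator as recipients. Leakage through conversation is possible but is conjecture.
- *Causality is judged after the code break.* 11.s puts the investigator's association assessment in the initial report when that report is a narrative, and unblinding may come at any time within 24 hours. The order is unspecified.
- *The chair must decide without knowing the allocation.* The point rests on omission. Nothing bars the chair from asking the pharmacy service, and section 13 offers conditional access.

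**Conclusion.** The point holds as a cheap improvement of modest impact. The text of 11.u states an automatic disclosure that is at odds with the double-blind design: any SAE, including an unrelated one, reveals the drug allocation to the person who reports the primary outcome, whether or not care requires it. The second part is a gap, not a prohibition: no provision gives the chair the allocation for the 11.v decision.

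On the assumed 1-3% SAE rate and 10-30 minute reporting shift, the expected movement in a drug-level mean is about 0.15 to 1.35 minutes against a 30-minute target, and less once dropout is counted. Both assumptions come from outside the documents. The finding on the wording of the rule does not depend on them.

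**What to change.** Reconcile 11.u and 11.v with the double-blind design in section 5:

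1. Replace automatic disclosure to the subject with a code break through the Investigational Drug Service on request, when the treating clinician or medical collaborator judges that the allocation is needed. Put no restriction on access by treating or emergency clinicians.
2. State in 11.v that the Investigational Drug Service gives the allocation confidentially to the advisory board chair on request for the discontinuation decision.
3. Require the investigator's relatedness assessment to be recorded before any code break, where the situation allows.
4. Record each unblinding (date, reason, recipients), and add to section 10.n a sensitivity analysis of total wake time that excludes diary data after unblinding. The intention-to-treat analysis stays primary.

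The cost is a rewording of two sections, one instruction to the pharmacy service and one added analysis. The downside is that subjects whose care does not depend on the code learn their allocation later than they would under the current rule.

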12.1.1 Possible Drug Interactions

Possible drug interactions with solriamfetol include:

- MAOIs (must have stopped the medication > 14 days ago)

ee. Benefits

As indicated in the research plan, participants in this study will likely experience improved sleep (less insomnia). The results of this study, it is hoped, will provide a novel approach to the treatment of insomnia that is as or more effective than traditional approaches and/or makes traditional treatments easier to follow.

ff. Risk Benefit Assessment

1. Risks:

Non-invasive procedures are proposed. It is possible that completion of questionnaires may cause some discomfort for participants due to the content of questions asked. Subjects may experience higher than normal levels of sleepiness due to the nature of CBT-I. The use of the internet for completion of study measures also introduces potential risks for confidentiality of personal data.

2. Benefits:

There may be no known benefits for participants in this study. This project serves to benefit the research community by providing data on insomnia treatment mechanisms. Subjects may experience a decrease in their insomnia and fatigue symptoms. The risks to the participants are believed to be outweighed by the benefit of conducting the research.

10. Informed Consent Process / HIPAA Authorization

Overview

Consent is done on an individual basis during the initial evaluation by a designated staff member via HIPAA compliant Zoom. Subjects will be asked to complete the consent in a private area. For the informed consent process, the details of the consent form are discussed, and the subject is encouraged to ask questions about study participation and any other details described in the consent form. Once signed, the subject is provided a copy of the consent form to keep.

Children and Adolescents

N/A

Adult Subjects Not Competent to Give Consent

Only competent adults will be included in this study.

i. Alterations to Typical Consent Process (only include if applicable) N/A

1. Waiver of Consent (In some cases for screening/portions of that study that qualify as minimal risk, a waiver of documentation of consent may be permissible per IRB SOPs) N/A

2. Waiver of Written Documentation of Consent N/A

3. Waiver of Written Documentation of Consent where the research is subject to FDA regulations N/A

4. Waiver of HIPAA Authorization N/A

j. Study Finances

a. Funding Source

This study is supported by an Axsome Pharmaceuticals

b. Conflict of Interest

All University of Pennsylvania Investigators will follow the University of Pennsylvania Policy on Conflicts of Interest Related to Research.

c. Subject Stipends or Payments

d. Compensation will be pro-rated for each component of the study for a total of \$500 per participant. Specifically, each participant will receive \$50 for completing the screening visit, \$25 for fully completing baseline sleep diaries, \$200 for fully completing all sleep diaries and questionnaires during the treatment period (8 weeks), \$100 for completing the study, and \$125 for completing the follow-up assessment.

k. Publication Plan

While the primary intent of the study is to garner effect size data, if the inferential statistics are significant with 5-8 subjects per condition, the data will be summarized as a short report for the journal SLEEP or the Journal of Sleep Research.

I. References

Relevant references were placed in text (PMID numbers). Also below.

1: 1. Perlis, M., Jungquist, C., Smith, M. T., & Posner, D. (2005). The cognitive behavioral treatment of insomnia: A treatment manual. Springer. ISBN-10: 0387222529, <https://www.amazon.com/Cognitive-Behavioral-Treatment-Insomnia-Session-ebook/dp/B000PC6BGA>

m. Attachments

- Sample Consent Form

a. Source Documents

The data is being acquired on-line. The original questionnaires are not retained, though they can be regenerated from the database data.

b. Case Report Forms (CRFs)

The data is being acquired on-line. The original questionnaires are not retained, though they can be regenerated from the database data.

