As noted above, side effects will be assessed in several ways: daily assessments via the sleep diaries and weekly evaluation with a medical symptom checklist (52 symptoms where positive endorsements allow subjects to rate their average severity and number of days affected).

10. Statistical Plan

k. Primary Endpoint

The primary endpoint is total wake time (time spent awake in bed) at the end of post-treatment, as measured via a web based self-report Sleep Diary.

I. Secondary Endpoints

1. Patients treated with CBT-I will have significantly greater improvements in sleep continuity from baseline to post-treatment compared to patients not administered CBT-I.
2. Patients treated with CBT-I in combination with solriamfetol will have significantly greater improvements in sleep continuity from baseline to post-treatment compared to patients treated with CBT-I alone.
3. Exploratory hypotheses: Patients treated with CBT-I in combination with solriamfetol will have significantly greater adherence with sleep restriction (i.e., sleep rescheduling, prescribed time to bed [PTTB]) and on daytime performance measures (e.g., ESS, FSS, etc.) compared to CBT-I alone.

m. Sample Size and Power Determination

To detect a clinically significant difference in self-reported total wake time of 30 minutes between the four treatment groups at the end of post-treatment using an ANOVA test, this study will require 10 subjects per group x 4 groups = 40 treatment completers. These calculations assume a standard deviation in total wake time of 19 minutes, with 80% power to detect the clinically significant change at an alpha level of .05. A total of 60 subjects will be recruited to obtain a sample of 40 subjects that complete the study due to attrition.

n. Statistical Methods

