Primary analyses will be conducted on an intention to treat basis and the trial conducted and reported according to CONSORT guidelines. Variable distributions will be examined to investigate homoscedasticity, outliers and normality, and corrected where appropriate using data transformations. The primary analysis is a 4(condition: +/- solriamfetol and +/- CBT-I) x 2(time: pre- and post-treatment) mixed ANOVA on absolute and percent change in total wake time ([TWT], time spent awake per night). If the interaction between condition and time is significant, Dunnett multiple comparisons will be conducted to further investigate differences in TWT between active treatment conditions versus the control condition to test Hypotheses 1-3. These analyses will be unadjusted in the first instance and then adjusted for covariates (primarily, age and sex).

An interim unadjusted analysis as per above will be conducted after 50% of the target sample have completed post-treatment (i.e., when N=20).

Secondary analyses include examining the interaction between treatment condition and time on other outcomes, including sleep continuity assessed via Sleep Diary (SL, WASO, EMA, TST, SE), insomnia (ISI), daytime sleepiness (ESS and KSS), fatigue (FSS and modified KSS), and daytime function (FOSQ-10, POMS, and PVT). Additionally, compliance to the medication (adherence to daily pill administration, as assessed via blister packs) and to sleep restriction (adherence to prescribed time to bed) will be investigated as covariates.

i. Baseline Data

Baseline and demographic characteristics will be summarized by standard descriptive statistics (including mean and standard deviation for continuous variables such as age and standard percentages for categorical variables such as gender).

ii. Pharmacokinetic Analysis **N/A**

iii. Interim Analysis **N/A**

iv. Safety Analysis

Side effects and adverse events will be assessed in several ways: daily assessments via the sleep diaries, and with a weekly evaluation using a medical symptoms checklist (52 symptoms where positive endorsements allow subjects to rate their average severity and number of days affected),

An adverse event will be defined as 1) any behavioral or health complaint spontaneously reported during the study, 2) an above threshold score on the study clinical assessment instruments (ESS, PHQ-9, or GAD-7), and/or a 20% increase in the medical symptom check list scores (frequency or severity).

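### The only report named in the publication plan is triggered by significance at 5-8 subjects per condition, below the planned 10, in a study said to be mainly about effect sizes; report the full sample whatever the result.

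*Combined protocol and SAP*

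**What the plan says.** Section k, Publication Plan, is a single sentence. It opens with a statement of purpose, "While the primary intent of the study is to garner effect size data", and continues with the trigger: "if the inferential statistics are significant with 5-8 subjects per condition, the data will be summarized as a short report". Two candidate journals are named. The sentence does not mention the full sample or a non-significant result.

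Three other places bear on it:

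- Section 10.m sizes the trial: "this study will require 10 subjects per group x 4 groups = 40 treatment completers". Its inputs are a 30-minute difference in total wake time (TWT), an SD of 19 minutes, 80% power and an alpha of .05.
- Section 10.n makes a general commitment that does not depend on the result: "the trial conducted and reported according to CONSORT guidelines". It also schedules an interim analysis at N=20, which is 5 per condition if the groups are balanced.
- Section 5.6 says that the study is powered for its primary hypothesis, solriamfetol versus placebo on TWT. That is a confirmatory aim, whereas the publication plan describes an estimation aim.

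**The concern.** A study meant to supply effect sizes should not let significance decide which effect sizes are published. An estimate that reaches print because it passed a significance test has been selected for being large, and the selection is stronger the smaller the sample. The trigger sits at 20-32 subjects, where the planned test is well short of its design power.

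The trigger can also operate as the trial is planned, because the N=20 analysis falls at the bottom of the 5-8 range. If a short report came out by this route, a later trial could be planned on an exaggerated solriamfetol effect. How exaggerated depends on which contrast is reported and on the true effect, so the size has to be worked out case by case.

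This is separate from the type I error of an interim look. Selection on significance biases the published estimate at any alpha.

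**Working it through.** **Inputs.** From section 10.m: difference 30 min ("To detect a clinically significant difference in self-reported total wake time of 30 minutes between the four treatment groups"), SD 19 min ("These calculations assume a standard deviation in total wake time of 19 minutes"), alpha .05, 80% power, 10 per group in four groups. From the publication plan: n = 5 to 8 per condition. Assumptions: balanced groups, SD 19 applied to the TWT measure analysed, two-sided contrasts, additive effects. A true effect of 15 min is not in the documents and serves only to show a range.

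**Step 1: reproduce the plan's sample size.** Take a one-way ANOVA with four groups, the extreme means 30 min apart and the other two at the midpoint. The noncentrality is λ = n × Σ(μᵢ − μ̄)² / SD² = n × (15² + 0 + 0 + 15²) / 19² = n × 450/361 = 1.247n. At n = 10, λ = 12.47 on 3 and 36 df, which gives power 0.811. The smallest n reaching 80% is 10, so the stated figure reproduces.

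**Step 2: power of the same test at the trigger sizes.**

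| n per condition | Power |
|---|---|
| 5 | 43% |
| 6 | 53% |
| 7 | 62% |
| 8 | 69% |
| 10 (planned) | 81% |

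This is the pattern of means that reproduces the plan's 10. Other patterns with a 30-min range give more power: if one group differs from the other three, 61% at n=5 and 87% at n=8.

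**Step 3: the Dunnett threshold.** For three comparisons with control, the two-sided 5% critical values (by simulation) are 2.591 at n=5 (16 df) and 2.486 at n=8 (28 df). The threshold is critical value × 19 × √(2/n):

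- n=5: 2.591 × 19 × √0.4 = 31.1 min
- n=8: 2.486 × 19 × √0.25 = 23.6 min

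These hold only if the observed SD is exactly 19. A smaller sample SD lets a smaller difference through.

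**Step 4: average estimate among results that pass.** The figures come from simulation with at least 200,000 replicates per setting. Section 10.n prescribes the F test first, then Dunnett comparisons with control. The pooled contrast is solriamfetol versus placebo averaged over CBT-I, tested at .05.

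| What must be significant | True solriamfetol effect | Mean at n=5 | Mean at n=8 |
|---|---|---|---|
| F, then Dunnett, solriamfetol alone vs control | 15 min (assumed) | 33-34 min | 28 min |
| Same | 30 min | 39 min | 34 min |
| Pooled solriamfetol vs placebo | 15 min (assumed) | 23 min | 19 min |
| Same | 30 min | 31.4 min | 30.2 min |
| F test only, with a true CBT-I effect of 30 min (assumed) | 15 min (assumed) | 15.9 min | 15.1 min |

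The first row is inflated about 2.2 times at n=5 (33.5/15) and 1.9 times at n=8 (28/15). The fourth row is inflated by 5% (31.4/30) and under 1% (30.2/30). The last row, for solriamfetol alone versus control, is inflated by 6% (15.9/15) and under 1% (15.1/15). The first two rows barely change whether the CBT-I effect is 0, 15 or 30 min.

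**The case against.** The strongest reply is that the sentence sets a sufficient condition for one short report, possibly an early one. It does not say that this is the only report, nor that null results will be withheld, and section 10.n commits to CONSORT reporting whatever the outcome. This stands. A reader might infer that a null result has no route to publication, but the documents do not say so. What remains is narrower: the CONSORT line names no report, sample or time, and the section that should name them names only the significance-triggered one.

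A second reply is that large inflation is not a general consequence of the trigger. This also stands. The publication plan refers to inferential statistics in general, so a CBT-I effect or the overall F test could trigger the report, and the solriamfetol estimate would then be almost unselected. On the pooled contrast at the plan's own 30 min, the bias is 5% or less.

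A third reply is that the data collected are unaffected. That is true: the bias lies in estimates published through the trigger, and no endpoint, allocation or sample size changes.

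It is also tempting to read the 31.1-min threshold as meaning that any publishable single-arm effect at n=5 must exceed 30 min. That is wrong, because the test uses the sample SD. Among n=5 results passing F and then Dunnett, about 31% are below 30 min when the truth is 15 min, and about 12% when it is 30 min.

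**Conclusion.** The point holds in a limited form. The publication plan names one report, conditions it on significance at 50%-80% of the planned group size, and does so in the sentence that declares effect-size estimation the main purpose. Following that trigger selects the published estimate.

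The resulting bias runs from negligible (pooled 30-min effect, or a CBT-I effect that carries the F test) to about a doubling (a true 15 min for solriamfetol alone versus control, passing F and then Dunnett). These sizes rest on SD 19, balanced groups and additive effects; the 15-min truth and the 30-min CBT-I effect are assumptions. The documents do not support a claim that null results will be suppressed, or that the published solriamfetol effect will necessarily be exaggerated.

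This should be corrected, but it is not a must-fix: it affects reporting, not the conduct or analysis of the trial.

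**What to change.** Replace the sentence in section k, Publication Plan, with wording such as:

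*Comparative results will be reported at the planned 40 completers (or at the final sample if recruitment ends early), whether or not they are significant, with estimates and 95% confidence intervals for every planned contrast. Significance at 5-8 subjects per condition will not trigger publication.*

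The clause on early closure keeps a smaller final sample reportable. Also reconcile the primary intent stated there with the powered hypothesis in section 5.6, so that the document says once whether the trial is confirmatory, estimation-focused, or both in a stated order.

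The cost is a text amendment and the loss of an early short report. Sample size, procedures and analyses do not change.
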